8.3.4. Regulatory Reporting Requirements for Serious Adverse Events

The sponsor assumes responsibility for appropriate reporting of AEs to the regulatory authorities. The sponsor will also report to the investigator (and the head of the investigational institute where required) all suspected unexpected serious adverse reactions (SUSARs). The investigator (or sponsor where required) must report SUSARs to the appropriate IEC/IRB that approved the protocol unless otherwise required and documented by the IEC/IRB. A SUSAR will be reported to regulatory authorities unblinded. Participating investigators and IEC/IRB will receive a blinded SUSAR summary, unless otherwise specified.

8.3.5. Pregnancy

All initial reports of pregnancy in participants or partners of male participants must be reported to the sponsor by the study-site personnel within 24 hours of their knowledge of the event using the appropriate pregnancy notification form. Abnormal pregnancy outcomes (eg, spontaneous abortion, fetal death, stillbirth, congenital anomalies, ectopic pregnancy) are considered SAEs and must be reported using an SAE reporting form. Any participant who becomes pregnant during the study must discontinue further study vaccination.

Follow-up information regarding the outcome of the pregnancy and any postnatal sequelae in the infant will be required.

8.3.6. Adverse Events of Special Interest

Adverse events of special interest (AESIs) are significant AEs that are judged to be of special interest because of clinical importance, known class effects, or based on nonclinical signals. AESIs will be carefully monitored during the study by the sponsor.

AESIs must be reported to the sponsor within 24 hours of awareness irrespective of seriousness (ie, serious and non-serious AEs) or causality following the procedure described above for SAEs.

Specific requirements for AESIs are described below.

8.3.6.1. Thrombosis With Thrombocytopenia Syndrome (TTS)

As described in Section 2.3.1, Risks Related to Study Participation, TTS has been observed very rarely following vaccination with Ad26.COV2.S and is considered to be an AESI in this study. TTS is a syndrome characterized by a combination of both a thrombotic event and thrombocytopenia.

Because this syndrome is rare and not completely understood, all cases of thrombosis and/or thrombocytopenia will be considered a suspected case of TTS until further adjudication can be performed. An AESI Adjudication Committee with appropriate expertise will be established to evaluate each suspected AESI and determine whether it is a case of TTS. The investigator shall be

responsible for reporting any suspected AESI of TTS using the SAE form and the form detailed in Section 10.12. A suspected TTS case is defined as:

- Thrombotic events: suspected deep vessel venous or arterial thrombotic events as detailed in Section 10.14 OR,
- Thrombocytopenia, defined as platelet count below 150,000/ μ L (BC 2021)

Symptoms, signs, or conditions suggestive of a thrombotic event should be recorded and reported as a suspected AESI even if the final or definitive diagnosis has not yet been determined, and alternative diagnoses have not yet been eliminated or shown to be less likely. Follow-up information and final diagnoses, if applicable, should be submitted to the sponsor as soon as they become available.

In the event of thrombocytopenia, study site personnel should report the absolute value for the platelet count and the reference range for the laboratory test used.

For either a thrombotic event or thrombocytopenia, testing for anti-PF4 should be performed at the local laboratory or substitute local laboratory; repeat testing may be requested for confirmation upon sponsor discretion.

Suspected AESIs will require enhanced data collection and evaluation (see Section 1.3.4.1). Every effort should be made to report as much information as possible about the AESI to the sponsor in a reasonable timeframe.

If an event meets the criteria for an SAE (Section 10.4.1), it should be reported using the same process as for other SAEs.

The form detailed in Section 10.12 is intended as a guide for assessment of the AESIs to facilitate diagnosis and determine treatment options. If the investigator is not the treating physician, every effort should be made to collect the information requested in the form from the treating physician and enter the available information in the eCRF. The sponsor will also attempt to collect information from any thrombotic event, thrombocytopenia, or TTS reported prior to protocol Amendment 1.

8.3.6.2. Multisystem Inflammatory Syndrome in Children

The Multisystem Inflammatory Syndrome in Children (MIS-C) is considered to be an AESI.

Unlike adults, the vast majority of children with COVID-19 have mild symptoms. However, some children have a significant respiratory disease, and some children may develop a hyperinflammatory response similar to what has been observed in adults with COVID-19.

The CDC issued a Health Advisory on May 2020, that outlines the following case definition for MIS-C (CDC, 2020):

- An individual aged <21 years presenting with fever^a, laboratory evidence of inflammation^b, and evidence of clinically severe illness requiring hospitalization, with multisystem (≥ 2) organ involvement (cardiac, renal, respiratory, hematologic, gastrointestinal, dermatologic, or neurological); AND
- No alternative plausible diagnoses; AND
- Positive for current or recent SARS-CoV-2 (COVID-19) infection by RT-PCR, serology, or antigen test; or COVID-19 exposure within the 4 weeks prior to the onset of symptoms.

In the event of a suspected (MIS-C) event, laboratory assessments ([AAP 2020](#); [CDC 2020](#); [Henderson 2020](#)) are required to facilitate diagnosis and determine treatment options, including but not limited to:

- Levels of inflammatory markers in the blood, including elevated erythrocyte sedimentation rate (ESR)/C-reactive protein (CRP) and ferritin, lactate dehydrogenase (LDH), and absolute lymphocyte count.
- Complete blood count and platelet count.
- B-type natriuretic peptide (BNP) or NT-proBNP (pro-BNP) and sodium,
- D-dimer

SARS-CoV-2 related syndromes in the pediatric population continues to evolve and recommendations provided in this document do not replace the importance of clinical judgment tailored to the unique circumstances of an individual patient.

8.4. Virology Assessments

The presence of SARS-CoV-2 infection in nasal swabs will be assessed by the local laboratory for case management. Molecular confirmation of SARS-CoV-2 infection (via molecular diagnostic RT-PCR or equivalent, referred to as ‘molecular test’ throughout the document) by a central laboratory will be used for the exploratory analysis of the case definition. Nasal swabs will also be used to determine the presence of SARS-CoV-2 viral variants using whole genome sequencing. In addition, saliva samples collected from participants during a confirmed COVID-19 episode may be tested for the presence of and quantification of SARS-CoV-2 by a central laboratory.

Nasal swabs collected from participants with COVID-19-like signs or symptoms will also be tested at the central laboratory to determine the presence of other respiratory pathogens using a broad respiratory pathogens panel. The results from this test may be shared with the study site.

^a Fever $>38.0^{\circ}\text{C}$ for ≥ 24 hours, or report of subjective fever lasting ≥ 24 hours.

^b Including, but not limited to, one or more of the following: an elevated C-reactive protein (CRP), erythrocyte sedimentation rate (ESR), fibrinogen, procalcitonin, D-dimer, ferritin, lactic acid dehydrogenase (LDH), or interleukin 6 (IL-6), elevated neutrophils, reduced lymphocytes, and low albumin.

8.5. Biomarkers

Blood will be drawn at selected timepoints during the study for evaluation of biomarkers (eg, related to vaccine immunogenicity and SARS-CoV-2 infection including relations with COVID-19 disease severity, PAXgene®), as indicated in Section 1.3.

8.6. Medical Resource Utilization and Health Economics

Health Economics/Medical Resource Utilization and Health Economics parameters are not evaluated in this study.

9. STATISTICAL CONSIDERATIONS

Statistical analysis will be done by the sponsor or under the authority of the sponsor. A general description of the statistical methods to be used to analyze the immunogenicity and safety data is outlined below. Specific details will be provided in the SAP.

9.1. Statistical Hypotheses

No formal hypothesis testing is planned in Part 1. Descriptive statistics will be used to compare vaccine immunogenicity in adolescents from study VAC31518COV3006 versus vaccine immunogenicity in young adults (18 to 25 years of age) from study VAC31518COV3001 or VAC31518COV3009 and between study groups in VAC31518COV3006. Descriptive statistics will be used to summarize the safety and reactogenicity endpoints.

9.2. Sample Size Determination

With a sample size of 50 participants per group, the width of the 90% CI for the observed proportion of adverse events will vary between 5.8% and 24.8% depending on the observed proportion. Assuming pooling of adverse event data after the first dose of the 1- and 2-dose regimen, the width of this confidence interval will vary between 3% and 17.3% depending on the observed proportion (Table 4).

Non-binding guidelines on dose and regimen selection will be described in the SAP. Decision making on the optimal regimen will take safety and reactogenicity data, as well as any available immunogenicity data, and data from other Janssen clinical trials of Ad26.COV2.S into account.

Table 4 : 90% Two-sided CI for Possible Observed Rate of Adverse Events

Observed Rate	0%	5%	10%	25%	50%
50 Participants	(0, 5.8%)	(1.2%, 13.4%)	(4%, 19.9%)	(15.3%, 37%)	(37.6%, 62.4%)
100 Participants	(0, 3%)	(2%, 10.2%)	(5.5%, 16.4%)	(18%, 33.1%)	(41.4%, 58.6%)

9.2.1. Immunogenicity

The VNA and S-ELISA have been selected as primary endpoints and samples from participants (young adults and adolescents) will be analyzed using these assays. Correlation between S-ELISA and VNA and between other relevant humoral immunogenicity readouts will be evaluated. See Section 9.4.2 for immunogenicity endpoints.

9.2.2. Safety

While mild to moderate vaccine reactions (local site and systemic responses) are expected, AEs that preclude further vaccine administration or more serious ones that would limit product development are not anticipated. The observation of 0 events (eg, SAEs) is associated with 95% confidence that the true event rate is below the rates specified in [Table 5](#) for the considered number of participants.

Table 5 : Upper Limit of the 95% One-sided CI if no Cases are Observed for Different Sample Sizes

Sample Size	N=25	N=50	N=100	N=250	N=1,000
Upper Limit 95% one-sided CI	11.3%	5.8%	3.0%	1.2%	0.3%

CI = confidence interval, N = number of participants

9.3. Populations for Analysis Sets

For purposes of analysis, the following populations are defined:

The Full Analysis Set (FAS) will include all participants with at least one vaccine administration documented.

The Per Protocol Immunogenicity (PPI^a) population will include all randomized and vaccinated participants for whom immunogenicity data are available excluding participants with major protocol deviations expected to impact the immunogenicity outcomes. In addition, samples obtained after missed vaccinations or samples obtained from participants after SARS-CoV-2 infection (if confirmed by molecular testing or non-S-ELISA [or equivalent assay]) occurring during the study after randomization (if applicable), after other SARS-CoV-2 vaccination outside the study, and samples obtained outside predefined windows will be excluded from the analysis set. Participants who were seronegative by local serology finger-prick test on Day 1 prior to study entry but were determined to be seropositive at baseline by central N- or S- serology testing will also be included in the PPI. More details will be provided in the SAP.

9.4. Statistical Analyses

The SAP will be finalized prior to the first database lock and it will include a more technical and detailed description of the statistical analyses described in this section. This section is a summary of the planned statistical analyses of the most important endpoints including primary and key secondary endpoints.

9.4.1. General Considerations

Analysis populations are defined in [Section 9.3](#). Planned analyses are defined in [Section 9.5](#).

^a If a participant would be vaccinated out of window due to a study pause, this will not by default be a reason for excluding this participant from the PPI. A sensitivity analysis might also be performed. Further details will be described in the SAP.

For safety and immunogenicity analyses, results will be analyzed by vaccine group and will be performed by age group in adolescents. Immunogenicity subgroup analyses will also be performed by BMI, ethnicity, and other factors as will be described in the SAP.

9.4.2. Primary/Secondary Endpoints

Safety Endpoints

No formal statistical testing of safety data is planned. Safety data will be analyzed descriptively by vaccine group and by age group (12 to 15, and 16 to 17). In addition, for selected tables, tabulations pooled by vaccine dose will also be provided. All safety analyses will be done on the FAS.

Adverse Events

The verbatim terms used in the eCRF by investigators to identify AEs will be coded using the Medical Dictionary for Regulatory Activities (MedDRA). All reported AEs will be included in the analysis. (S)AEs caused by molecularly confirmed SARS-CoV-2 infection will be removed at the analysis level from the (S)AE listings and tables and presented separately. For each AE, the percentage of participants who experience at least one occurrence of the given event will be summarized by vaccine group.

Summaries, listings, datasets, or participant narratives may be provided, as appropriate, for those participants who die, who discontinue study vaccine due to an AE, or who experience a severe AE, AESI, or an SAE (including MIS-C).

Solicited local (at injection site) and systemic AEs will be summarized descriptively. The number and percentages of participants with at least one solicited local (at injection site) or systemic AE will be presented. The frequencies by vaccine group as well as frequencies according to severity and duration will be described for solicited AEs. Frequencies of unsolicited AEs, separately for all and vaccination-related only, will be presented by System Organ Class and preferred term, while those of solicited AEs will be presented only by preferred term.

Vital Signs

Vital signs including temperature, pulse/heart rate, preferably supine systolic and diastolic blood pressure, and respiratory rate will be summarized over time, using descriptive statistics and/or graphically. The percentage of participants with values beyond clinically important limits will be summarized.

Physical Examinations

Physical examination findings will be summarized at baseline. A listing of the abnormalities will be made.

Immunogenicity Endpoints

Descriptive statistics (geometric mean and confidence intervals, or median and interquartile range Q1-Q3, as appropriate) will be calculated for continuous immunologic parameters. Several

definitions of serological response will be applied (fold increases in GMC [ELISA] or GMT [VNA]). Graphical representations of immunologic parameters will be made as applicable. Frequency tabulations will be calculated for discrete (qualitative) immunologic parameters, as applicable.

In addition, the ratio between neutralizing and binding antibodies as determined by VNA and S protein ELISA, respectively, will be calculated together with confidence intervals. More details will be provided in the SAP.

S-ELISA or VNA may be used as endpoint for decision making on dose and regimen selection. Correlation between S-ELISA and VNA and between other relevant humoral immunogenicity readouts will be evaluated.

The immunogenicity analyses will be performed on the PPI population.

COVID-19 Infections and Severity

Symptomatic and asymptomatic infections will be descriptively presented.

Descriptive analysis will be performed for the results of the SIC and results of diagnostic tests for SARS-CoV-2 infection after screening. Further details will be provided in the SAP.

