Functional and molecular antibody characterization	Analysis of antibody characteristics including, but not limited to avidity, Fc-mediated viral clearance, Fc characteristics, Ig subclass, IgG isotype, antibody glycosylation, and assessment of antibody repertoire
Epitope-specificity characterization	Analysis of site-specificity, epitope mapping
Cytokine profiling	Analysis of cytokines, chemokines, and other proteins of the immune response in serum or plasma
Passive transfer	Analysis of immune mediators correlating with protection against experimental SARS-CoV-2 challenge in a suitable animal model
Gene expression analysis (RNA-seq)	Analysis of gene expression by RNA transcript profiling

ELISA = enzyme-linked immunosorbent assay; Fc = crystallizable fragment; Ig = immunoglobulin; SARS-CoV-2 = severe acute respiratory syndrome coronavirus-2; MSD = Meso Scale Diagnostics, LLC; RBD = receptor binding domain; RNA = ribonucleic acid; VNA = virus neutralization assay

a. Either Spike-ELISA or VNA will be used to support the primary endpoint in Part 1.

A rapid SARS-CoV-2 serologic finger-prick test for past infection with SARS-CoV-2 will be performed for all participants at Day 1. Participants who test positive will be informed of the result by the study staff.^a Participants who test positive will not be included.

^a Vaccination with Ad26.COV2.S may interfere with some serologic assays utilized at local community health clinics/commercial laboratories, by seeking and identifying the spike protein in the vaccine and rendering a false positive result. For this reason, participants will be encouraged to not seek testing outside the study. If a participant requires testing outside of the protocol-mandated testing schedule, the site will guide them on the appropriate assay that identifies the viral nucleocapsid protein (and not the spike protein).

Biomarker Evaluations

For participants with a positive molecular test result for SARS-CoV-2 infection, biomarker analysis (PAXgene, RNA-seq) may be performed for evaluation of COVID-19 cases and to explore potentially informative biomarkers, eg, those associated with severe COVID-19.

Safety Evaluations

After each vaccination, participants will remain under observation at the study site for at least 30 minutes (or longer if required by institutional/local practice) for the presence of any acute reactions and solicited events.

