From the time of local approval of protocol Amendment 1 onwards, TTS (Section [8.3.6.1](#)) and MIS-C (Section [8.3.6.2](#)) are considered to be AESIs. Suspected AESIs (thrombotic events and thrombocytopenia [defined as platelet count below 150,000/ μ L] [[BC 2021](#)], and MIS-C) will be recorded from the moment of vaccination until the end of the study/early withdrawal. An AESI Adjudication Committee with appropriate expertise will be established to evaluate each suspected AESI and determine cases of TTS (Section [8.3.6](#)).

Serious Adverse Events

All SAEs, as well as PQC, occurring during the study must be reported to the appropriate sponsor contact person by study-site personnel within 24 hours of their knowledge of the event.

Serious adverse events, including those spontaneously reported to the investigator, must be reported using an SAE form. The sponsor will evaluate any safety information that is spontaneously reported by an investigator beyond the time frame specified in the protocol.

Information regarding SAEs will be transmitted to the sponsor using the Serious Adverse Event Form and Safety Report Form of the eCRF, which must be completed and reviewed by a physician

from the study site, and transmitted to the sponsor within 24 hours. The initial and follow-up reports of an SAE should be transmitted electronically or by facsimile (fax). Telephone reporting should be the exception and the reporter should be asked to complete the appropriate form(s) first.

Signs and symptoms of MIS-C will be monitored and reported as SAE in adolescents with (suspected) COVID-19 as confirmed by a positive molecular test result for SARS-CoV-2, and in adolescents whose parents/caregivers or close relatives/contacts have a prior (within 4-weeks) or current suspected or confirmed COVID-19. Further details on case definition and reporting of MIS-C in adolescents can be found in Section 10.8.

8.3.2. Method of Detecting Adverse Events, Medically-attended Adverse Events, Adverse Events of Special Interest, and Serious Adverse Events

Care will be taken not to introduce bias when detecting AEs, MAAEs, suspected AESIs, or SAEs. Open-ended and nonleading verbal questioning of the participant is the preferred method to inquire about AE occurrence.

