10.4.1. Adverse Event Definitions and Classifications

Adverse Event

An AE is any untoward medical occurrence in a clinical study participant administered a pharmaceutical (investigational or non-investigational) product. An AE does not necessarily have a causal relationship with the study vaccine. An AE can therefore be any unfavorable and unintended sign (including an abnormal finding), symptom, or disease temporally associated with the use of a medicinal (investigational or non-investigational) product, whether or not related to that medicinal (investigational or non-investigational) product. (Definition per International Conference on Harmonisation [ICH])

This includes any occurrence that is new in onset or aggravated in severity or frequency from the baseline condition, or abnormal results of diagnostic procedures, including laboratory test abnormalities.

Any respiratory tract infection that is not due to SARS-CoV-2 will be reported as an AE if it occurs between the time of any vaccination through the following 28 days. Any respiratory tract infection recorded as an AE in the eCRF will be excluded from any AE analysis if the molecular test is subsequently found to be positive for SARS-CoV-2. Respiratory tract infections arising from SARS-CoV-2 infection will not be reported as (S)AEs in the Clinical Study Report but will be tabulated separately. In general, any (S)AEs caused by molecularly confirmed SAR-CoV-2 infection will be removed at the analysis level from the (S)AE listings and tables and presented separately.

Note: For time period of sponsor's AE collection, see All Adverse Events under Section [8.3.1](#).

Serious Adverse Event

An SAE based on ICH and EU Guidelines on Pharmacovigilance for Medicinal Products for Human Use is any untoward medical occurrence that at any dose:

- Results in death
- Is life-threatening
(The participant was at risk of death at the time of the event. It does not refer to an event that hypothetically might have caused death if it were more severe.)
- Requires inpatient hospitalization or prolongation of existing hospitalization
- Results in persistent or significant disability/incapacity
- Is a congenital anomaly/birth defect
- Is a suspected transmission of any infectious agent via a medicinal product

- Is Medically Important*

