10.9. Appendix 9: Case Definitions for COVID-19

10.9.1. Case Definitions for Adolescents 12 to 17 Years of Age

10.9.1.1. Case Definition for Moderate to Severe/Critical COVID-19

Case Definition for Moderate COVID-19

- A SARS-CoV-2 positive RT-PCR or molecular test result from any available respiratory tract sample (eg, nasal swab sample, sputum sample, throat swab sample, saliva sample) or other sample

AND at any time during the course of observation until signs and symptoms disappear:

Any 1 of the following new or worsening signs or symptoms:

- Respiratory rate ≥ 20 breaths/minute
- Abnormal saturation of oxygen (SpO_2) but still $>93\%$ on room air at sea level*
- Clinical or radiologic evidence of pneumonia
- Radiologic evidence of DVT
- Shortness of breath or difficulty breathing

Any 2 of the following new or worsening signs or symptoms:

- Fever ($\geq 38.0^{\circ}\text{C}$ or $\geq 100.4^{\circ}\text{F}$)
- Heart rate ≥ 90 beats/minute
- Shaking chills or rigors
- Sore throat
- Cough
- Malaise as evidenced by 1 or more of the following**:
 - Loss of appetite
 - Generally unwell
 - Fatigue
 - Physical weakness
- Headache
- Muscle pain (myalgia)
- Gastrointestinal symptoms (diarrhea, vomiting, nausea, abdominal pain)**
- New or changing olfactory or taste disorders
- Red or bruised looking feet or toes
- Other nonspecific symptoms such as: rash, bloodshot eyes or eye irritation/drainage

OR

* SpO_2 criteria will be adjusted according to altitude per investigator judgement.

** Having 2 or more elements of a symptom (eg, vomiting and diarrhea or fatigue and loss of appetite) is counted only as 1 symptom for the case definition. To meet the case definition, a participant would need to have at least 2 different symptoms.

Case Definition for Severe/Critical COVID-19

- A SARS-CoV-2 positive RT-PCR or molecular test result from any available respiratory tract sample (eg, nasal swab sample, sputum sample, throat swab sample, saliva sample) or other sample

AND any 1 of the following at any time during the course of observation:

- Clinical signs at rest indicative of severe systemic illness (respiratory rate ≥ 30 breaths/minute, heart rate ≥ 125 beats/minute, oxygen saturation [SpO_2] $\leq 93\%$ on room air at sea level*, or partial pressure of oxygen/fraction of inspired oxygen [$\text{PaO}_2/\text{FiO}_2$] < 300 mm Hg)
- * SpO_2 criteria will be adjusted according to altitude.

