 - Positive for current or recent SARS-CoV-2 (COVID-19) infection by RT-PCR, serology, or antigen test; or COVID-19 exposure within the 4 weeks prior to the onset of symptoms.

The AESI will be reported from the moment of vaccination until the end of the study/early withdrawal. An AESI Adjudication Committee with appropriate expertise will be established to evaluate each suspected AESI and determine cases of TTS.

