5.7.1.3. Analysis of Adverse Events

The number and percentage of participants with at least one particular AE (unsolicited/solicited) will be tabulated.

Unsolicited AEs will be summarized by System Organ Class and Preferred Term. Solicited AEs will be summarized by class (administration site, systemic) and preferred term.

For solicited AEs, the following tables will be provided: summary, by worst severity grade, at least grade 3, related (systemic only), at least grade 3 related, time to onset (in days) from the start of each vaccination period and duration (in days) for most frequent events (>5%) and body temperature. Note: Duration is defined as number of days from the start of the event until resolution of the event. The time to first onset is defined as (date of first onset – reference date + 1). The reference dates are the start dates of all prior vaccination periods (i.e. the prior vaccination dates for dose 1, dose 2 and/or Booster).

For unsolicited AEs, the following tables will be provided: summary table (including SAE, AESIs, MAAEs, MAAEs leading to study discontinuation, fatal outcome, and discontinuation), all events, most frequent (>5%), at least grade 3, related, at least grade 3 related, and SAE. The proportion of AEs resulting in a medically attended visit (other than routine health maintenance visits) will also be tabulated.

Selected tables will be repeated by SARS-CoV-2 by serostatus at baseline [or in seronegative subgroup only if there are less than 5% of seropositive subjects], and overall.

Listings and/or participant narratives will be provided as appropriate, for those participants who die, discontinue study due to an AE, experience a SAE, or AESI.

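### The rule taking COVID-19-caused (S)AEs out of the main safety tables has no exception for AESIs, conflicts with the primary SAE and AESI endpoints, and is not carried into the SAP

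*Protocol*

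**What the plan says.** - **Endpoints.** Protocol 3 and SAP 1.1 list SAEs and AESIs, the latter expressly including MIS-C, as primary safety endpoints from first vaccination to the end of the study. Neither excludes events linked to infection.
- **Analysis rule.** Protocol 9.4.2 first says "All reported AEs will be included in the analysis". The next sentence is the removal rule: "S)AEs caused by molecularly confirmed SARS-CoV-2 infection will be removed at the analysis level from the (S)AE listings and tables and presented separately". Protocol 10.4.1 repeats, as a general rule, that they "will be removed at the analysis level from the (S)AE listings and tables and presented separately".
- **MIS-C.** Protocol 8.3.1 says: "Signs and symptoms of MIS-C will be monitored and reported as SAE in adolescents with (suspected) COVID-19", where a molecular test confirms the infection, and likewise in adolescents whose contacts have suspected or confirmed disease. Protocol 8.3.6.2 makes MIS-C an AESI.
- **Thrombosis.** Protocol 8.3.6.1 treats any thrombosis or thrombocytopenia as suspected TTS until adjudicated. Protocol 10.9.1.1 lists "Radiologic evidence of DVT" among the signs that, with a positive test, make a moderate COVID-19 case.
- **SAP.** Section 5.7.1.3 plans, for unsolicited AEs, a "summary table (including SAE, AESIs, MAAEs, MAAEs leading to study discontinuation, fatal outcome, and discontinuation") and a separate SAE table. It plans no separate AESI table. It offers listings or narratives for SAEs and AESIs as appropriate, and does not mention the removal rule. Section 6.2 records changes to protocol-planned analyses as not applicable.

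**The concern.** The removal rule reaches events that the study names as primary endpoints. MIS-C follows SARS-CoV-2 infection, so the case with the firmest evidence of infection, a positive molecular test, is the one the rule can move. The same can happen to a thrombosis in a PCR-positive participant, although TTS is a recognised risk of this vaccine (Protocol 2.3.1).

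Moving such an event depends on its being caused by the infection, and no document says who decides this or by what criteria. Protocol 10.4.2 asks the investigator only about the relation to study vaccine.

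At stake is whether the headline SAE and AESI counts by dose group are complete. There is no placebo arm, and SAP 5.8.2 states that harm monitoring therefore cannot be done. The tables by dose group are thus the main place where a reader would look for severe events after vaccination.

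**Working it through.** **1. Tracing one PCR-confirmed MIS-C through the documents**

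| Step | Source | Result |
|---|---|---|
| Reporting | Protocol 8.3.1, 8.3.6.2 | SAE and AESI |
| Endpoint | Protocol 3, SAP 1.1 | Counts for both primary endpoints |
| Tables under the protocol | 9.4.2, 10.4.1 | Out of the (S)AE tables if judged caused by the infection; shown separately |
| Tables under the SAP | 5.7.1.3 | Rule absent; read alone, in the SAE table and in the AESI line of the unsolicited-AE summary |
| Separate display | SAP 5.8.3 | Infection counts, N-serology, symptom data and narratives, all at the final analysis; the listed narrative contents include no AE or SAE item |

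The protocol promises a separate presentation, but the SAP section nearest to it does not describe a table of COVID-19-caused (S)AEs and applies only at the final analysis. The primary analysis, on data to 28 days post-dose 2 (SAP 5.9), has no such display specified.

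**2. The plan's own safety bound**

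Protocol 9.2.2, Table 5, bases its assurance on zero observed events. The exact one-sided 95% upper limit is 1 − 0.05^(1/n):

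- n = 25: 11.29% (stated 11.3%)
- n = 50: 5.82% (stated 5.8%)
- n = 100: 2.95% (stated 3.0%)
- n = 250: 1.19% (stated 1.2%)
- n = 1,000: 0.30% (stated 0.3%)

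Table 5 reproduces in full.

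**3. What a moved event does to that bound**

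For k events the exact upper limit is the 0.95 quantile of Beta(k+1, n−k). The value of k is an assumption, because the documents give no rate for MIS-C or thrombosis in this population. The sizes are one group (50), two groups pooled by dose (100) and the whole study (300).

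| n | k = 0 (event moved out) | k = 1 (event kept) | k = 2 |
|---|---|---|---|
| 50 | 5.82% | 9.14% | 12.06% |
| 100 | 2.95% | 4.66% | 6.16% |
| 300 | 0.99% | 1.57% | 2.08% |

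Check of k = 1, n = 50 at p = 0.0914: (1−p)^50 + 50·p·(1−p)^49 ≈ 0.008 + 0.042 = 0.05.

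**The case against.** The strongest reply is that the events are displaced, not lost. The rule itself promises separate presentation. Protocol 9.4.2 goes on to name AESIs and SAEs, MIS-C included, among the events for which summaries, listings or narratives may be given. SAP 5.8.3 adds a narrative for each confirmed COVID-19 case. AESIs reach the sponsor within 24 hours (8.3.6), and a possibly vaccine-related MIS-C triggers a pause and IDMC review (6.8). All of this stands. A reader might infer that an MIS-C could go unreported; the documents do not support that.

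Four other stronger readings also fail.

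- **That all MIS-C leaves the tables.** Only molecularly confirmed events judged to be caused by infection move. Cases resting on serology, antigen test or exposure stay, and MIS-C may appear weeks after an unrecognised infection (10.8).
- **That the AESI count certainly loses the event.** The rule names (S)AE listings and tables. The loss is inferred from SAP 5.7.1.3, which has AESIs only as a line in the unsolicited-AE summary.
- **That the SAP contradicts the protocol.** Silence is not a contrary rule, and the declaration of no change in 6.2 fits the protocol rule still applying. Table mock-ups sit in the Data Presentation Specifications, which are not available here.
- **That vaccine-induced serology alone could make a case of MIS-C.** The infection criterion does accept "Positive for current or recent SARS-CoV-2 (COVID-19) infection by RT-PCR, serology, or antigen test", without naming the serology target, and the protocol warns: "Vaccination with Ad26.COV2.S may interfere with some serologic assays". But the definition also requires fever, laboratory inflammation, severe illness needing hospitalization, at least two organ systems and no alternative diagnosis. Serology can meet one criterion only.

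The study is also descriptive, and the dose guidelines in SAP 5.9.1 use Grade 3 local and systemic events and will not be assessed in this study. The point therefore does not bear on those guidelines.

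**Conclusion.** The concern holds as a conflict between an analysis rule and two primary safety endpoints, and as a gap in the SAP. Protocol 9.4.2 and 10.4.1 contain no AESI exception, the deciding judgement of causation by infection is undefined, and the SAP specifies neither the rule nor the separate display. The two documents together do not settle which tables will be produced.

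The numerical effect is an illustration only. If one such event occurred and were moved, the reported upper limit would be lower by 3.3 percentage points in a group of 50 (9.14% − 5.82%) and by about 0.6 points in 300 (1.57% − 0.99%). This rests on one event, on molecular confirmation, on attribution to infection, and on a reader taking the bound from the main table alone. Few such events should be expected. The importance is moderate.

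**What to change.** 1. In Protocol 9.4.2 and 10.4.1 and in SAP 5.7.1.3, state that all SAEs, all AESIs (MIS-C, suspected and adjudicated TTS) and all deaths are tabulated by group regardless of SARS-CoV-2 status. Add a second table that excludes infection-attributed events.
2. State who judges that an event was caused by the infection, on what criteria, and where this is recorded. Protocol 8.3.6.1 and 10.3.6 charge the adjudication committee with TTS only, while 10.13 speaks of adjudicating MIS-C; these passages need to be reconciled.
3. Specify the separate COVID-19 display in the SAP: contents, groups, and whether it is produced at the primary analysis as well as the final one.
4. Leave the MIS-C case definition as it is, since it is a clinical definition tied to AESI reporting and to a pausing rule. For each MIS-C case, record which evidence met the infection criterion: PCR, antigen, N-serology, S-serology or exposure. Reconcile the unspecified serology in that criterion with the protocol's own warning about spike-based tests.

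The cost is a few sentences in each document, one extra table and one recorded item per MIS-C case. The downside is that some COVID-related events will appear in the vaccine safety tables and need a footnote.
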